### 11. Safety and Acceptance Evaluation

# 11.1 Adverse Events

The adverse events are some unintended symptoms, physical signs, or health conditions that show up during the whole trial. They may have no causality with the interventions. A health condition or an illness existing before the trial can be deemed as an adverse event (AE) if the situation becomes worse within the study period. An abnormal result of the laboratory examination can be deemed as an AE only if it causes some clinical symptoms and need related therapies. We observe the adverse events by asking the participants non-inducing questions at each assessing point. We also observe the adverse events through participants' self-report, or through physical examination, or by laboratory examination. All the adverse events must be record at length on the CRF.

#### **EA Related Adverse Events**

Adverse events will be recorded and measured both by participants themselves and acupuncturists. Acupuncturists are responsible for the recording of the EA-related adverse events on the CRF. The adverse events relating to acupuncture include broken needle, nausea during acupuncture, faint caused by needling during the treatment, unbearable pricking (VAS≥7) caused by needling during the treatment, Sharp pain lasting more than one hour (VAS≥4) after acupuncture, hematoma or bleeding around the site of needling, numbness or infection around the site of needling, sleeplessness after acupuncture, dizziness after acupuncture, other discomforts (including palpitation, headache, loss of appetite, drowsiness, or aggravation of existing symptoms) after acupuncture. Acupuncturists will record the symptoms, frequency, degree, and the duration of

each AE. The pricking caused by needling will be assessed through 10-point visual analog scale (VAS).

## Prucalopride Related Adverse Events

Diarrhea, nausea, abdominal pain, abdominal distention, vomiting, dyspepsia, inappetence, flatulence, abnormal bowel sound, hemoproctia, dizziness, headache, tremor, palpitation, myocardial ischemia/infarction, prolonged QT interval, frequent micturition, fatigue, fever.

### 11.2 Acceptance Evaluation of EA

We will evaluate the acceptability of acupuncture for the EA group. The acceptability of acupuncture will be evaluated through a point system as following:

- 0= hard to accept;
- 1= a little hard to accept;
- 2= acceptable;
- 3= easy to accept;
- 4= very easy to accept.

The scores of acceptability will be recorded after 5 minutes of the first and tenth treatment (the score will be summed up and divided by 2). If the participant drops out after the first treatment, then the score recorded of the first treatment will be used.

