### Manipulation:

After sterilizing the skin in supine position, needles with the size of 0.30mm×50mm, or 0.35mm×75mm will be inserted into ST25 and SP14 slowly and vertically, without manipulation, for approximately 30-70mm until they pierce into the muscle layer of the abdominal wall. Needles with the size of 0.30mm×40mm will be inserted into ST37 vertically for about 25mm. If BL33 is needed, all points could be simultaneously needled when participants are in the lateral decubitus position. The needle is inserted at BL33 inwardly and downwardly at an angle of 30-45 degree to a depth of 50–60mm. For DU20 and DU24, the needle is obliquely inserted backwards into the galea aponeurotica to a depth of 40mm.

Paired alligator clips of the EA apparatus will be attached transversely to the needle holders of bilateral ST25 and SP14 (and BL33 if needed). EA stimulation will last for 30 minutes with a dilatational wave of 10/50 Hz and current intensity of 0.5-2.0mA. The skin around the acupoints shivering mildly indicates the proper dose. For ST37 (and DU20, DU24 if needed), three small equal manipulations of twirling, lifting and thrusting will be performed. The participants' feeling of soreness and/or distention indicates the proper manipulation of deqi. The twirling, lifting and thrusting manipulation should be performed every 10 minutes, three times, in 30 minutes. Course of treatment:

Each participant will accept an 8-continuous-week treatment with 28 sessions in total. The participants will be treated 30 minutes for each session, once a day, five times per week in the first two weeks, and three times per week in the latter 6 weeks.

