## Acceptance evaluation of EA:

We will evaluate the acceptability of acupuncture for the EA group. The acceptability of acupuncture will be evaluated through a point system as following:

- 0= hard to accept;
- 1= a little hard to accept;
- 2= acceptable;
- 3= easy to accept;
- 4= very easy to accept.

The scores of acceptability will be recorded after 5 minutes of the first and tenth treatment (the score will be summed up and divided by 2). If the participant drops out after the first treatment, then the score recorded of the first treatment will be used.

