#### 1. Study Objective

The objective of this trial is to evaluate if the effect of EA is non-inferior to prucalopride for SCC. In addition, If the therapeutic efficacy of EA could sustain for 3 months or 6 months? The safety and acceptance of EA will be simultaneously evaluated.

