### Manipulation:

After sterilizing the skin in participants with supine position, needles of the size of 0.30mm×50mm, or 0.35mm×75mm will be inserted into ST25 and SP14 slowly and vertically, without manipulation, for

approximately 30-70mm until they pierce into the muscle layer of the abdominal wall. Needles of the size of 0.30mm×40mm will be inserted in to ST37 vertically for about 25mm. If BL33 is needed, all points could be simultaneously needled when participants are in the lateral position. The site 0.5-1cm outside and above the 3rd posterior sacral foramina will serve as the inserting site. The needle is inserted at the inserting site inwardly and downwardly at an angle of 30-45 degree to a depth of 50–60mm. For DU20 and DU24, the needle is obliquely inserted back towards the galea aponeurotica to a depth of 40mm.

Paired alligator clips of the EA apparatus will be attached transversely to the needle holders of the bilateral ST25 and SP14 (and BL33 if needed). EA stimulation will last for 30 minutes with a dilatational wave of 10/50 Hz and current intensity of 0.5-2.0mA. The skin around the acupoints shivering mildly indicates the proper dose. For ST37 (and DU20, DU24 if needed), three small equal manipulations of twirling, lifting and thrusting will be performed. The participants' feeling of sore and distention show the proper manipulation of deqi. The twirling, lifting and thrusting manipulation should be performed every 10 minutes, three times in 30 minutes.

Each participant will accept an 8-continuous-week treatment with 28 sessions in total. The participants will be treated 30 minutes once, once a day, five times per week in the first two weeks, and three times per week in the latter 6 weeks.

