#### 12. Compliance Assessment

The adherence of participants towards treatments were counted via the EA sessions or prucalopride tablets they have received. Prucalopride tablets were recycled back from the participants every two weeks in treatment period and every four weeks in follow-up period, and the number of tablets were documents in CRF by outcome assessors.

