- (10) Post-hoc analyses: A weekly CSBM responder was defined as a patient who had ≥3 CSBMs for a given week and an increase from baseline of ≥1 CSBM for that same week. An overall CSBM responder was a patient who was a weekly CSBM responder for at least 6 of the 8 treatment weeks (75%). A sustained CSBM responder met the overall responder criteria, and also met the responder criteria for at least 3 of the last 4 treatment weeks. For proportion of the overall CSBM responder and sustained CSBM responder over weeks 1-8, Chi-square tests were used. For the weekly CSBMs and its changes from baseline of each week for data collection (week -2, week -1, weeks 1-8, weeks 11-12, weeks 15-16, weeks 19-20, weeks 31-32), a repeated measures analysis of variance was used, setting group, time, and the interaction of group and time as the fixed effects; besides, the baseline CSBMs data and usage of rescue medicine were set as the covariate.
- (11) For the acceptability of EA, the number and proportion of participants who accepted the treatment of electroacupuncture was describe.

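### EA acceptability is rated only at sessions 1 and 10 and early leavers keep their session-1 score, so an objective covering an 8-week course is answered from weeks 1-2 and people who gave up EA can be counted as accepting it

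*Supplement*

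**What the plan says.** SAP section 1 and final protocol 2.3 make acceptance an objective: "The safety and acceptance of EA will be simultaneously evaluated".

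SAP 11.2 and final protocol 2.4.8.3 measure it on a five-point scale from 0 to 4. Scores 0 and 1 are worded as degrees of difficulty in accepting EA, and 2 is the lowest score worded as acceptable. On timing: "The scores of acceptability will be recorded after 5 minutes of the first and tenth treatment". The two scores are added and halved. For those who leave early: "If the participant drops out after the first treatment, then the score recorded of the first treatment will be used".

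On the course of treatment, SAP 7.2 and final protocol 2.4.6.2 say: "Each participant will accept an 8-continuous-week treatment with 28 sessions in total", given "five times per week in the first two weeks, and three times per week in the latter 6 weeks".

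On analysis, SAP 13.6(11) says only that "the number and proportion of participants who accepted the treatment of electroacupuncture was describe". It gives no score that counts as accepting, no denominator, and no role for stopping EA. Sessions attended are recorded under SAP 12 ("The adherence of participants towards treatments were counted via the EA sessions or prucalopride tablets they have received"), but nothing links that count to the acceptability result.

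**The concern.** The objective concerns a 28-session, 8-week regimen, while the measure covers only its first two weeks. Three features make the result hard to interpret.

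- **No late rating.** Nothing is asked in weeks 3-8, which are also the primary-outcome window. Someone who stops EA in those weeks keeps a score from weeks 1-2.
- **Averaging.** A fall between sessions 1 and 10 is blended into one number that can still look favourable.
- **Score kept after leaving.** A participant who rates EA 3 after session 1 and abandons it at session 6 because of the needling stays at 3. The score predates the reason for leaving, and stopping EA never enters the measure.

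At stake is the reported proportion who accepted EA. It could be higher than the experience of the whole course would justify, and it cannot be reproduced from the plan, because 'accepted' is not defined.

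**Working it through.** **Inputs.** Five sessions a week in weeks 1-2, three a week in weeks 3-8, 28 in all (SAP 7.2). Ratings at sessions 1 and 10, averaged (SAP 11.2). Recruitment of 560 with a 20% dropout allowance (SAP 9) and 1:1 allocation (SAP 4), so 560 / 2 = 280 in the EA arm.

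**Step 1: reproduce the plan's figure and place session 10.** 5 x 2 + 3 x 6 = 10 + 18 = 28, as stated. Session 10 = 5 x 2, the last session of week 2. Sessions after the last rating: 28 - 10 = 18, and 18 / 28 = 64%. Weeks after it: 8 - 2 = 6.

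**Step 2: what averaging can hide.** Take a mean of 2 or more as accepting. This is an assumption drawn from the scale wording. The pairs (session 1, session 10) that end at 0 or 1 yet still count as accepting are:

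- 3 then 1: (3 + 1) / 2 = 2.0
- 4 then 0: (4 + 0) / 2 = 2.0
- 4 then 1: (4 + 1) / 2 = 2.5

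**Step 3: leaver against stayer.** A participant who scores 4 and quits before session 10 keeps 4. One who scores 4, stays and then scores 0 gets 2. The rule can rank the person who gave up EA above the one who continued.

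**Step 4: possible size of the leaver effect.** Compared with counting those who leave before session 10 as not accepting,

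overstatement = (share leaving before session 10) x (share of those leavers scoring 2 or more at session 1).

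The documents give neither share. With 280 in the EA arm and the second share running from 0 to 1:

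| Assumed share leaving before session 10 | People | Overstatement (points) |
|---|---|---|
| 2% | 6 | 0 to 2.1 |
| 5% | 14 | 0 to 5.0 |
| 10% | 28 | 0 to 10.0 |
| 20% | 56 | 0 to 20.0 |

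The 20% row puts the whole planned dropout allowance before session 10 and is only an outer bound. The overstatement is zero if the leavers scored 0 or 1 at session 1.

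**Step 5: link to adherence.** SAP 13.2 treats failure to complete 23 or more sessions as a major protocol violation. A participant who stops at session 12 therefore leaves the per-protocol set but contributes an unmodified acceptability score.

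**The case against.** **The rule does not class leavers as accepting.** It keeps whatever they scored, and a leaver at 0 or 1 stays there. This stands. A reader might infer that everyone who gave up EA is counted as accepting it. The documents do not support that: it can happen only when the session-1 score was high enough, and without a cut-off in SAP 13.6(11) no participant's class is settled.

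**The direction of bias is not shown.** A first experience of deep abdominal needling could be the worst-rated session, with acceptance rising later. This stands for those who remain in treatment. A reader might conclude that acceptance is certainly biased upwards; the documents give no basis for a direction in weeks 3-8. For early leavers an upward effect is plausible but conditional on their first score.

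**Tolerability is captured elsewhere.** EA sessions are counted (SAP 12). Adverse events, including severe pricking and lasting pain, are recorded (SAP 11.1), and intervention-related events are summarised (SAP 13.7). Someone who left because of needling pain would probably appear there. It is therefore too strong to say that the objective cannot be addressed at all. But none of these sources asks whether the participant found the course acceptable, and none feeds the acceptability figure.

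**Counting procedure-related stopping as non-acceptance is one definition among several.** It mixes a patient's rating with adherence and tolerability. This stands, so it belongs in a sensitivity analysis and not in the main result.

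**Follow-up contact would threaten blinding.** Non-adherent participants are followed by the outcome evaluators (final protocol 2.4.7.4), who are to be blinded (final protocol 2.4.4). Asking about EA would reveal allocation. This stands and determines who should collect the extra rating.

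**Conclusion.** The point holds as a cheap improvement. The arithmetic is exact: 18 of 28 sessions (64%) and six of eight weeks follow the last rating. Averaging can hide a decline, and the early-leaver rule can count people who gave up EA as accepting it.

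The size rests on assumptions: a cut-off of 2, an unknown share leaving before session 10, and an unknown share of those with a first score of 2 or more. On those terms the overstatement is 0-5 points at 5% leaving and 0-10 points at 10%. Quoting only the upper ends would be wrong. The 20% in the sample-size section is an overall allowance and says nothing about EA dropout in weeks 1-2.

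A reader might also infer that the main finding is at risk. It is not. The item is descriptive, confined to the EA arm, and separate from the non-inferiority comparison.

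**What to change.** In final protocol 2.4.8.3, SAP 11.2 and SAP 13.6(11):

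1. Repeat the same 0-4 rating at the last EA session attended (session 28, or when EA is stopped). Unblinded treatment staff should collect it, not the blinded outcome evaluators.
2. Report the distributions at session 1, session 10 and the last session separately, in place of the mean.
3. Define 'accepted' as a score of 2 or more, and state the denominator at each rating.
4. Drop the rule that substitutes the session-1 score. Show beside each rating the number who had stopped EA before it, with reasons.
5. Add a sensitivity analysis that counts stopping for a procedure-related reason as not accepting.

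The cost is one extra question per EA participant and a few lines of SAP text. The acceptance figure may come out less favourable. Some who simply cease attending will have no last rating, but they will appear in the count of those who stopped. If data collection is already over, sessions 1 and 10 can still be reported separately beside the number who stopped EA, using scores and session counts that the plan already collects.

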#### 12. Compliance Assessment

The adherence of participants towards treatments were counted via the EA sessions or prucalopride tablets they have received. Prucalopride tablets were recycled back from the participants every two weeks in treatment period and every four weeks in follow-up period, and the number of tablets were documents in CRF by outcome assessors.

#### 13. Statistical Analysis

### 13.1 Objective and Hypothesis

#### Objective

Through comparing the efficacy of EA and prucalopride, we aim to evaluate if the effect of EA will be non-inferior to that of prucalopride. We also will evaluate if the therapeutic effect of EA could sustain for 3~6 months.

#### **Hypothesis**

The primary outcome is the proportion of participants with 3 or more mean weekly CSBMs. The non-inferior margin of the primary outcome is set as -10%.

H0: AEA-BPrucalopride <-10%; H1: AEA-BPrucalopride >-10%.

# 13.2 Statistical Analysis Set

Modified intention-to-treat (mITT) set will be defined as all the participants who accept randomization with baseline data. Per-protocol (PP) set will be composed of all randomly assigned participants without major protocol violations, which defined as the participants in EA group who were unable to complete 23 or more of the EA sessions, or the participants in control group who take prucalopride less than 180 days; or the participants who use prohibited medications and others which will be deemed to affect the interpretation of the primary outcome.

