### 2.4.6.3 Prucalopride Group

Participants will take Prucalopride Succinate (Janssen S.P.A) orally at a dose of 2 mg/day before breakfast for 8 weeks. Participants will undergo an electrocardiogram (ECG) at the 8th week, and the drug will be taken for another 24 weeks if no QT interval elongation or other severe cardiac adverse events (like myocardial infarction, severe arrhythmia, etc.). The use of other medicine for constipation will not be allowed during the trial. Prucalopride will be distributed to the participants beforehand every 2 weeks in the treatment period, and every 4 weeks in the follow-up period. The untaken pills will be recycled on the day of next distribution.

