### 7.2 Statistical Analysis Set

Modified intention-to-treat (mITT) set will be defined as all the participants who accept randomization with baseline data. Per-protocol (PP) set will be composed of all randomly assigned participants without major protocol violations. Major protocol violations are defined as participants in EA group who were unable to complete 23 or more of the EA sessions, or the participants in control group who take prucalopride less than 180 days; or the participants who use prohibited medications and others which will be deemed to affect the interpretation of the primary outcome.

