#### 7.3 Prucalopride Group

Prucalopride Succinate (Janssen S.P.A) will be taken orally at a dose of 2 mg/day before breakfast for 8 weeks. Participants will undergo an electrocardiogram (ECG) at the 8th week, and the drug will be taken for another 24 weeks in the absence of QT interval elongation or other severe cardiac adverse events (like myocardial infarction, severe arrhythmia, etc.). The use of other medicine for constipation will not be allowed during the trial. Prucalopride will be distributed to the participants beforehand every 2 weeks in the treatment period, and every 4 weeks in the follow-up period. The untaken pills will be recycled on the day of next distribution.

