#### **10.2 Primary Outcome**

The primary outcome is the proportion of participants with 3 or more mean weekly CSBMs over weeks 3–8. Assessing time frame: the latter 6 weeks of treatment (weeks 3-8).

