#### 13.5 Primary Outcome

The primary outcome was the proportion of participants with 3 or more mean weekly CSBMs over weeks 3-8. The Cochran-Mantel-Haenszel (CMH) test, stratified by center, was used to test a hierarchical comparison between two groups.

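### The only per-protocol set judges prucalopride adherence over 180 days and EA adherence over 8 weeks, although the primary outcome is fixed at week 8

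*Supplement*

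**What the plan says.** SAP 13.5 sets the endpoint: "The primary outcome was the proportion of participants with 3 or more mean weekly CSBMs over weeks 3-8". SAP 13.2 then defines a single PP set. In one arm it excludes "the participants in EA group who were unable to complete 23 or more of the EA sessions", in the other "the participants in control group who take prucalopride less than 180 days". Final protocol 7.2 has the same control-arm rule: "or the participants in control group who take prucalopride less than 180 days". Users of prohibited medication, and others judged to compromise interpretation of the primary outcome, are also excluded.

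The two treatment courses differ in length. For EA, SAP 7.2 says: "Each participant will accept an 8-continuous-week treatment with 28 sessions in total". Prucalopride is taken "orally at a dose of 2 mg/day before breakfast for 8 weeks" (SAP 7.3). After an ECG at week 8, final protocol 2.4.6.3 adds that "the drug will be taken for another 24 weeks if no QT interval elongation or other severe cardiac adverse events".

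Under SAP 13.3, missing primary-outcome data in the mITT population are multiply imputed, and the PP results serve as the check on that analysis. No other sensitivity analysis is named for the primary outcome. Neither document defines a second PP set for the follow-up outcomes, limits the 180-day rule to them, or exempts a stop that the continuation condition requires.

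**The concern.** A PP set for a weeks 3-8 outcome should reflect whether participants were treated as planned up to week 8. Here the EA criterion does so and the control criterion does not. A control participant who took every tablet through week 8 and has a complete diary is still removed if the drug is stopped soon afterwards. Nothing taken after day 56 can change that participant's outcome.

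The exclusion falls on one arm and depends on later behaviour that may be related to response: people may stop because the drug has not helped, because of side effects, or because they feel well. In a non-inferiority trial readers look to agreement between the mITT and PP results for reassurance. With this rule the two can agree or disagree for reasons unrelated to the effect of EA. The rule also discards observed outcomes, so it does little to test the missing-at-random assumption that the PP result is meant to check.

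**Working it through.** **Inputs.** EA: 28 sessions in 8 weeks, threshold 23 (SAP 7.2, 13.2). Prucalopride: 8 weeks plus a conditional 24 weeks, threshold 180 days (SAP 7.3, 13.2). Good compliance: at least 80% (final protocol 5.3). Planning control rate 30.9% and margin -10 points (SAP 9).

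**1. Where the thresholds come from.**
- EA: 5 × 2 + 3 × 6 = 28 sessions. 0.80 × 28 = 22.4, rounded up to 23; 23/28 = 82.1%.
- Prucalopride: 56 + 168 = 224 days. 0.80 × 224 = 179.2, rounded up to 180; 180/224 = 80.4%.

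Both figures reproduce as 80% of the arm's full planned course.

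**2. Position relative to the endpoint.**
- The outcome window closes on day 8 × 7 = 56.
- All 28 EA sessions are scheduled by then.
- At most 56 days of drug can have been taken by then, so 180 - 56 = 124 further days are needed. The threshold cannot be met before 180/7 = 25.7 weeks.
- A participant who took 56 of 56 days and does not continue because of the week-8 ECG has 56 days, and is a major violator as written.

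**3. Threshold on the endpoint's own window.** 0.80 × 56 = 44.8, so at least 45 days. At the EA arm's exact fraction, 23/28 × 56 = 46.

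**4. Possible shift in the PP control rate.** The documents give no stopping rates, so those below are assumptions. Let dR and dN be the fractions of weeks 3-8 responders and non-responders who fall short of 180 days. Then

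PP rate = 0.309(1 - dR) / [0.309(1 - dR) + 0.691(1 - dN)]

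| dR | dN | Calculation | PP control rate | Shift (points) |
|---|---|---|---|---|
| 10% | 20% | 0.2781 / (0.2781 + 0.5528) | 33.5% | +2.6 |
| 10% | 30% | 0.2781 / (0.2781 + 0.4837) | 36.5% | +5.6 |
| 20% | 10% | 0.2472 / (0.2472 + 0.6219) | 28.4% | -2.5 |
| equal | equal | common factor cancels | 30.9% | 0 |

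These are illustrations, not bounds: more unequal rates give larger shifts (dR = 30%, dN = 10% gives 25.8%, or -5.1). They move the control arm only, and they count anyone short of 180 days, including people who stopped before day 56 and might fail a week-8 rule too.

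**The case against.** The best defence is that one standard is applied to both arms. Final protocol 5.3 defines compliance as treatment received over treatment planned, with 80% as the threshold, and both PP criteria follow from it. This stands. A reader who sees 180 days beside 8 weeks might infer a laxer rule for EA, but the arithmetic does not support that. The fault is a mismatch with the endpoint window.

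A reader might also infer that the primary conclusion is at risk. It is not: the SAP rests the primary result on the imputed mITT analysis with a centre-stratified CMH test, and nowhere requires the PP set to show non-inferiority as well.

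Nor can the illustrated shifts be read as bias in the between-arm difference. The EA PP set drops non-completers too. If the 10% and 30% pattern also held there, 31.67% would become 0.2850 / (0.2850 + 0.4783) = 37.3%, or +5.7 points, and the net shift would be near zero. EA losses over 8 weeks may well be smaller than drug losses over 26 weeks, but the documents do not say.

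Final protocol 6.7 and 6.8 have analysis-set membership agreed at a data review meeting before lock, where stops following the ECG could be discussed. That is a partial safeguard; it does not alter the written rule.

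Finally, any PP set conditions on post-randomisation behaviour, including the one proposed below. The criticism is therefore narrower: this set conditions, in one arm, on events after the outcome is already fixed.

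**Conclusion.** The definition is wrong as written for the primary outcome and should be fixed, but it affects a supporting analysis only. The timing mismatch is certain from the text: at least 124 days of post-endpoint intake are required in the control arm and no post-endpoint treatment in the EA arm. So is the conflict between the PP definition and the conditional continuation of prucalopride; those passages must be reconciled.

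The size of the effect on the PP result cannot be computed from the documents. Under the assumed stopping rates, in the control arm alone and from 30.9%, the illustrated range is about -2.5 to +5.6 points against a 10-point margin, and zero if responders and non-responders stop equally. The direction is not fixed. If mainly non-responders stop, the PP control rate rises and non-inferiority becomes harder to show, which is conservative for the trial's claim. If mainly responders stop, the PP control rate falls and the PP result flatters EA. A reader might infer a bias in favour of EA; the documents do not support one.

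**What to change.** In SAP 13.2 and final protocol 7.2, define the PP set for the primary outcome by adherence and prohibited-medication use through the end of week 8 in both arms, with the same 80% rule: at least 23 of 28 EA sessions, or at least 45 of 56 prucalopride days. Keep the 180-day criterion only for a separate PP set for the follow-up outcomes. State there that a stop directed by the protocol's own continuation condition is not classed as a violation, so that the analysis-set text and the treatment text agree.

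The cost is a sentence or two in each document. Tablets are already counted every two weeks during treatment (SAP 12; final protocol 2.4.9), so no new data are needed. Only the analysis-set definition changes, not treatment.
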